MCM (defined as a composite of all major MCMs) among live and non-live offspring: The first primary outcome of interest is MCM occurring in live or non-live offspring. MCM is defined as defects of prenatal origin that have either cosmetic or functional significance to the child's health, development, or survival. MCM ascertainment will be based on the presence of an ICD-10 code (or other database specific coding system [codes to be adapted to the coding systems used in each of the data sources]) in the database. These ICD-10 codes will be classified according to the EUROCAT (Description of the Congenital Anomaly Subgroups in EUROCAT Guide 1.5) classification scheme, as four of the five data sources are in Europe (41). As there are some differences in the classification of MCMs by different classification schemes, the USA CDC definition of MCM as an abnormality of body structure or function that is present at birth, is of prenatal origin (i.e., birth defect), has significant medical, social, or cosmetic consequences for the affected individual, and typically requires medical intervention as implemented by the Metropolitan Atlanta Congenital Defects Program (MACDP) will also be implemented as a sensitivity analysis (see Section 9.7.5) (15, 24). The list of the MCM and their respective ICD-10 codes are presented in Table 22a using the EUROCAT classification. The MACDP 6-digit code defect list for major congenital malformations is presented in Table 22b.

The MCM ascertainment period is defined as:

- for live births, from birth until 1 year of age
- for non-live births (spontaneous abortion and stillbirth) an ICD-10 of MCM as the diagnosis at end of pregnancy
- for elective terminations, an ICD-10 code of an MCM as the reason for the termination at termination of pregnancy.

Select pregnancy loss outcomes (composite of spontaneous abortion and stillbirth) among all pregnancies

The second primary outcome of interest is select pregnancy loss outcomes, a composite of spontaneous abortion and stillbirth (Table 24).

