For the select pregnancy loss outcomes, the **index date/start of follow-up**, will be defined as the LMP2 (as defined in Section 9.1) from which the pregnancy will be followed until the outcome of interest. The **exit date/end of follow-up**¹¹ will be defined as the end of the study period, death, emigration (where available), loss to follow-up (disenrollment/de-registering), or date of first diagnosis of the outcome at study, or delivery, whichever is the earliest.

The select pregnancy loss outcomes will be defined as the presence of at least one of the following criteria:

- ICD-10 code of spontaneous abortion¹² (unintended loss of an intrauterine pregnancy) which is less than 22 weeks of gestation for the European data sources (40); less than 20 weeks for the USA data sources (64);
- ICD-10 code of stillbirth¹³ (unintended foetal death occurring at or after 22 weeks of gestation for the European data sources (78); at or after 20 weeks for the USA data sources (64).

Secondary outcomes

During the outcome ascertainment period, outcome events will be identified based on ICD-10 CM codes for the USA, ICD-10 for Denmark, Finland and France; MedDRA codes for Germany recorded in patient registries.

Minor congenital malformations

For this outcome the **index date/start of follow-up**, will be defined as the LMP2 (as defined in Section 9.1) from which the foetus/offspring will be followed up for the outcome of interest. The **exit date/end of follow-up** will be defined as the end of the study period, death, emigration (where available), loss to follow-up (disenrollment/de-registering), reaching the age of 1 year or date of first diagnosis of the outcome at study, whichever is the soonest.

¹¹ Specific outcome censoring rules will be applied. For spontaneous abortion outcome specific end of follow-up will be 22 weeks of gestation for the European data sources or 20 weeks for the USA data sources further details will be specified in the SAP.

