- **Spontaneous abortions**¹²: unintended loss of an intrauterine pregnancy which is less than 22 weeks of gestation for the European data sources (40); less than 20 weeks for the USA data sources (64);
- **Ectopic pregnancy:** occurs when a fertilised egg implants outside of the uterus, usually in one of the fallopian tubes.
- **Elective termination of pregnancy:** is defined as the intentional termination of pregnancy at any time in gestation for any reason. When possible, reasons for elective termination are captured and classified as elective termination of pregnancy for foetal anomaly or for other reasons.
- **Stillbirth**¹³: unintended foetal death occurring at or after 22 weeks of gestation for the European data sources (78); at or after 20 weeks for the USA data sources (64).
- **Composite of foetal loss:** will be defined as the presence of at least one of the following: spontaneous abortion, ectopic pregnancy, elective termination of pregnancy and stillbirth.
- **Infections requiring hospitalisation during pregnancy:** infections requiring hospitalisation during pregnancy will be considered as the occurrence of the first event of a hospitalisation for an infection diagnosis, as primary diagnosis. The list of the infections considered, and their respective ICD-10 codes are presented in [Table 24](#).
- **Emergency caesarean section:** surgical procedure involving the incision of the walls of the abdomen and uterus for delivery of an offspring that occurs when vaginal delivery is

¹⁴ Specific outcome censoring rules will be applied. For spontaneous abortion and ectopic pregnancy there will be outcome specific end of follow-up dates. For spontaneous abortion outcome specific end of follow-up will be 22 weeks of gestation as for the ectopic pregnancy end of follow-up will be 16 weeks of gestation further details will be specified in the SAP.

¹⁵ To maximize the capture of non-live births for spontaneous abortion, elective termination, and stillbirth, an exhaustive list of codes related to pregnancies as well as to outcomes will be used, i.e., every code will be included.

discontinued due to unexcepted complications during labour, such as the occurrence of foetal distress (105).

Adverse birth outcomes

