9.5.1.1 Assumptions used for the sample size and power calculations

To estimate the number of anifrolumab exposed SLE pregnancies and the expected number of primary study outcome events in data sources that would be eligible for the analysis in this study, the following assumptions were used:

- **A prevalence of 7% for MCM outcome.** Prevalence of MCM in pregnancies in women with moderate-to-severe SLE was estimated based on a literature search. Among moderate/severe SLE patients exposed to belimumab, birth defect prevalence estimates of 5.6% to 21.7% were observed in post hoc summary of clinical studies and a prospective

pregnancy registry, respectively (86) A prevalence of 6.4% of congenital malformations was observed in renal SLE pregnancies (51) These proxy estimates of MCM in moderate-to-severe SLE align with the observed population based prevalence estimates ranging from 7.4% to 13.6% (114) among women diagnosed with SLE (117).

- **A prevalence of 20% for the composite of select pregnancy loss outcomes (composite of spontaneous abortion and stillbirth).** Prevalence of the composite outcome of select pregnancy loss (spontaneous abortion and stillbirth) in moderate-to-severe SLE pregnancies ranged from 15.3% to 30% (51, 81, 86). For the individual outcomes, the prevalence estimates ranged from 1.8% to 3.7% for stillbirths (51, 103, 120), and the prevalence estimate was 16% (12.1% to 19.9%) for spontaneous abortions (103). Based on the intended objective to evaluate embryo-foetal loss, a composite outcome of spontaneous abortion and stillbirth has been used.
- **Proportion of SLE pregnancies occurring in women with moderate-to-severe disease of 50%.** There is limited information on the proportion of SLE pregnancies that occur in women with moderate-to-severe disease. The proportion of moderate-to-severe disease at the time of diagnosis among the general SLE population is estimated to be 50% (66, 80). Literature regarding medication patterns for SLE pregnant women suggests that 40-45% use immunosuppressors and/or biologics, which may be a proxy indicator of moderate/severe disease (12, 67). Thus, in this study, an assumption of 50% was used.

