Appendix D. Exemplar Codelists

Codelists included in this appendix are still under development and will be finalised in the SAP.

Table 18: Inclusion and exclusion criteria for the overall study population, EXEMPLARY codelist

Inclusion criteria for the overall source population	ICD-10
Systemic lupus erythematosus	
Systemic lupus erythematosus with organ or system involvement	M32.1
Other forms of systemic lupus erythematosus	M32.8
Systemic lupus erythematosus, unspecified	M32.9
Exclusion criteria for the overall source population	ICD-10
Multifetal pregnancies	
Multiple gestation	O30
IVF	
In vitro fertilisation	Z31.2

Abbreviations used in the table: ICD-10, International statistical classification of diseases tenth revision; IVF, In vitro fertilisation

Table 19: Drug classes and active substances used in SLE SOC ¹

Drug/Procedure	ATC codes
Antimalarials	
Chloroquine	P01BA01
Hydroxychloroquine	P01BA02
Quinacrine (mepacrine)	P01AX05
Glucocorticoids	
Dexamethasone	H02AB02
Methylprednisolone	H02AB04
Prednisolone	H02AB06
Prednisone	H02AB07
Triamcinolone	H02AB08
Immunosuppressive agents	
Biologic immunosuppressants	
Anifrolumab (drug of interest)	L04AA51
Belimumab	L04AA26
Rituximab (including reference product and biosimilars)	L01FA01
Synthetic immunosuppressants	
Anakinra	L04AC03
Apremilast	L04AA32
Azathioprine	L04AX01
Baricitinib	L04AA37
Cyclophosphamide	L01AA01
Cyclosporine	L04AD01
Leflunomide	L04AA13

Drug/Procedure	ATC codes
Methotrexate	L04AX03
Mycophenolic acid/sodium ¹	L04AA06
Sirolimus	L04AA10
Tacrolimus	L04AD02
Thalidomide	L04AX02
Tofacitinib	L04AA29
Voclosporin	L04AD03
Immunoglobulins	
Immunoglobulin G	J06BA02
Plasmapheresis	
Plasmapheresis (procedure)	B05AX03

Abbreviations used in the table: ATC, Anatomical therapeutic chemical classification system

¹ drugs that have been investigated in failed SLE clinical trials have not been included in the list of SLE SOC drugs. The list does not consider emerging therapeutic agents (in phase II/III development), of which the efficacy in the management of SLE has not been established.

² As Mycophenolate Mofetil.

Table 20: Confirmed teratogenic drugs

This list has been developed and will be continually updated based on the data available in the TERIS database of teratogenic agents and recent publications ([44](#), [88](#), [109](#), [122](#))

Drug Class	Generic Name	ATC code	Half Life	Pre-Conception Exposure Window ¹	Relevant Exposure Window

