Elective termination of pregnancy	Medical abortion	O04
	Other abortion	O05
	Unspecified abortion	O06
Stillbirth	Foetal death of unspecified cause	P95
	Single stillbirth	Z37.1
	Maternal care for hydrops foetalis	O36.2
	Maternal care for intrauterine death	O36.4
Infections requiring hospitalisation during pregnancy	Cholera	A00
	Typhoid and paratyphoid fevers	A01
	Other salmonella infections	A02
	Shigellosis	A03
	Other bacterial intestinal infections	A04
	Other bacterial foodborne intoxications, not elsewhere classified	A05
	Amoebiasis	A06
	Other protozoal intestinal diseases	A07
	Viral and other specified intestinal infections	A08
	Other gastroenteritis and colitis of infectious and unspecified origin	A09
	Respiratory tuberculosis, bacteriologically and histologically confirmed	A15
	Respiratory tuberculosis, not confirmed bacteriologically or histologically	A16
	Tuberculosis of nervous system	A17
	Tuberculosis of other organs	A18
	Miliary tuberculosis	A19
	Plague	A20
	Tularaemia	A21
	Anthrax	A22
	Brucellosis	A23
	Glanders and melioidosis	A24
	Rat-bite fevers	A25
	Erysipeloid	A26
	Leptospirosis	A27
	Other zoonotic bacterial diseases, not elsewhere classified	A28
	Leprosy [Hansen disease]	A30
	Infection due to other mycobacteria	A31
Listeriosis	A32	
Tetanus neonatorum	A33	

Adverse outcomes	Description	ICD-10
	Obstetrical tetanus	A34
	Other tetanus	A35
	Diphtheria	A36
	Whooping cough	A37
	Scarlet fever	A38
	Meningococcal infection	A39
	Streptococcal sepsis	A40
	Other sepsis	A41
	Actinomycosis	A42
	Nocardiosis	A43
	Bartonellosis	A44
	Erysipelas	A46
	Other bacterial diseases, not elsewhere classified	A48
	Bacterial infection of unspecified site	A49
	Congenital syphilis	A50
	Early syphilis	A51
	Late syphilis	A52
	Other and unspecified syphilis	A53
	Gonococcal infection	A54
	Chlamydial lymphogranuloma (venereum)	A55
	Other sexually transmitted chlamydial diseases	A56
	Chancroid	A57
	Granuloma inguinale	A58
	Trichomoniasis	A59
	Anogenital herpesviral [herpes simplex] infection	A60
	Other predominantly sexually transmitted diseases, not elsewhere classified	A63
	Unspecified sexually transmitted disease	A64
	Nonvenereal syphilis	A65
	Yaws	A66
	Pinta [carate]	A67
	Relapsing fevers	A68
	Other spirochaetal infections	A69
	Chlamydia psittaci infection	A70
	Trachoma	A71
	Other diseases caused by chlamydiae	A74
	Typhus fever	A75
	Spotted fever [tick-borne rickettsioses]	A77
	Q fever	A78
	Other rickettsioses	A79
	Acute poliomyelitis	A80

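### The exemplary stillbirth codelist includes O36.2 (care for foetal hydrops), which does not denote a death, so pregnancies ending in live birth could count as losses

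*Protocol*

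**What the plan says.** Section 9.3.2 introduces the second primary outcome and refers the reader to Table 24: "The second primary outcome of interest is select pregnancy loss outcomes, a composite of spontaneous abortion and stillbirth". The event rule follows: "The select pregnancy loss outcomes will be defined as the presence of at least one of the following criteria". Each criterion is an ICD-10 code, and stillbirth is described as "unintended foetal death occurring at or after 22 weeks of gestation for the European data sources", with 20 weeks in place of 22 for the USA sources. Follow-up ends at the first diagnosis of the outcome if that comes before delivery or censoring.

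Table 24 in Appendix D lists four stillbirth codes: P95 (foetal death, cause unspecified), Z37.1 (single stillbirth), O36.4 ("Maternal care for intrauterine death") and O36.2 ("Maternal care for hydrops foetalis"). A footnote in Section 9.3.2, aimed at capturing as many non-live births as possible, states that "an exhaustive list of codes related to pregnancies as well as to outcomes will be used, i.e., every code will be included".

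Table 24 is headed as exemplary, and Appendix D opens with the statement "Codelists included in this appendix are still under development and will be finalised in the SAP".

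**The concern.** Three of the four codes say that the foetus died. The fourth says that the mother received care because the foetus had hydrops. No outside source is needed to see the difference, because care for intrauterine death has its own line in the same list.

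Nothing in the protocol requires O36.2 to occur with a death code or a non-live outcome. Read as written, a pregnancy coded O36.2 and later ending in live birth becomes a stillbirth and leaves follow-up at that code. It counts in the select pregnancy loss composite and in the separate stillbirth and foetal-loss outcomes. If mother and child are linked, the same pregnancy is a live birth in the birth cohort. It enters the infant cohort only if born at 37 weeks or later, since Table 5 excludes earlier births there.

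The list is also used for adjustment. Table 21 assigns Table 24 to the previous-stillbirth covariate, which Table 7 lists as a potential confounder for congenital malformations and for stillbirth.

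False events that are equally common in both groups pull the RR towards 1. That is the unfavourable direction when the aim is to rule out an RR of 2.5.

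**Working it through.** **Inputs from the protocol (Section 9.5.1.1 unless noted).** Composite: "A prevalence of 20% for the composite of select pregnancy loss outcomes". Stillbirth prevalence: 1.8% to 3.7%, midpoint (1.8 + 3.7)/2 = 2.75%. Margin: RR 2.5. Required exposed pregnancies for the composite (Section 9.5.2): 72 at 1:2 and 61 at 1:3, for 80% power at one-sided 2.5%.

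**The plan's own figure.** With the Poisson variance of the log RR, n exposed = (1.960 + 0.842)² × (1/p + 1/(kp)) / (ln 2.5)², with p = 0.20 and k comparators per exposed pregnancy.
- k = 2: 7.849 × 7.5 / 0.8396 = 70.1, against 72 stated.
- k = 3: 7.849 × 6.667 / 0.8396 = 62.3, against 61 stated.

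Simulating the steps of Section 9.5.1.3 gives 81.7% power at 72 and 79.0% at 61. The stated sizes reproduce within tolerance. They rest on an assumed 20% and not on the codelist, so removing O36.2 does not change them.

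**Effect of the code if equally frequent in both groups.** Let h be the share of pregnancies that carry O36.2 and end in live birth. The documents give no value; 0.25% to 1% is an assumption. Observed RR = (RR × p + h) / (p + h).

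| h | Composite, p = 20%, true RR 2.0 | Composite, true RR 2.5 | Stillbirth, p = 2.75%, true RR 2.0 |
|---|---|---|---|
| 0.25% | 0.4025/0.2025 = 1.99 | 0.5025/0.2025 = 2.48 | 0.0575/0.0300 = 1.92 |
| 0.5% | 0.405/0.205 = 1.98 | 0.505/0.205 = 2.46 | 0.0600/0.0325 = 1.85 |
| 1% | 0.410/0.210 = 1.95 | 0.510/0.210 = 2.43 | 0.0650/0.0375 = 1.73 |

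At h = 1%, the two ends of the protocol's stillbirth range give 0.046/0.028 = 1.64 (at 1.8%) and 0.084/0.047 = 1.79 (at 3.7%).

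Relative inflation of the event count is h/p. For the composite it is 0.25/20 = 1.25% to 1/20 = 5%. For stillbirth it is 0.25/3.7 = 7% to 1/1.8 = 56%.

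**Effect if unequally frequent.** Take a true RR of 1.0 and h of 1% in one group and 0.25% in the other. Stillbirth at 2.75% is then seen as 0.0375/0.0300 = 1.25, or as 0.80 with the groups reversed. The composite is seen as 0.2100/0.2025 = 1.04, or as 0.96.

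**Error rate at the margin.** This uses the numbers expected at 10% exposure (163, 162, 145 and 11 exposed; 1:2), the Poisson standard error of Section 9.5.1.3 and a true composite RR of 2.5. The simulated chance of ruling out 2.5 is 0.8% without the code and 2.2% when 1% of non-loss pregnancies carry it. It reaches 4.8% at 2%, which is outside the range assumed above.

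**The case against.** The strongest reply is that the list is provisional. It is marked exemplary, is to be finalised in the SAP, and will be adapted source by source, with MedDRA terms for the German register. The text definition is foetal death, and a footnote adds that each data source's own definition applies. The Danish and Finnish birth registers record live births and stillbirths directly, and the German register records pregnancy outcome. On that view a draft code conflicts with a sound definition, and the exposure lies mainly in the claims-based sources.

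The provisional status stands: a reader should not infer that such pregnancies will be scored as stillbirths in the final analysis. It does not dispose of the point. This is a wrong entry in print, not a detail left for later, and the every-code footnote points towards carrying it forward.

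A second reply is that the primary comparison is hardly affected. That also stands for the assumed range. The simulated error rate at 1% stays under the nominal 2.5%, but this offers limited comfort. It starts at 0.8% because the Poisson model standard error is wide for binomial data, and Section 9.7.1 also allows log-binomial or robust Poisson models.

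A third reply is that the footnote shows a deliberate choice to maximise capture, so deletion might lose true deaths. The documents give no figure either way. This is a reason to prefer a conditional rule over plain deletion, not a reason to keep the code unconditionally.

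**Conclusion.** The definitional conflict holds: O36.2 does not denote a death, yet it sits in the stillbirth list under a rule by which one code makes an event.

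The size depends on an assumed frequency of 0.25% to 1% in both groups. For the 20% composite the dilution is slight. For stillbirth alone, in Objectives 8-9, it is material.

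Two stronger readings are tempting and are not supported. One is that the code seriously undermines the ruling out of RR 2.5. That margin is set for the primary outcomes, where a true 2.5 would be seen as 2.48 to 2.43; the larger dilution belongs to a secondary outcome with no such margin. The other is that the bias must run towards 1. That needs equal frequency of O36.2 in the two groups, which the documents do not establish.

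**What to change.** Before the codelist is finalised in the SAP, do one of the following in the stillbirth block of Table 24:

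- delete O36.2; or
- count O36.2 only when the same pregnancy also carries O36.4, P95 or Z37.1, or has a recorded non-live outcome.

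Carry the change into the source-specific code mappings, including the MedDRA mapping, and into the previous-stillbirth covariate that draws on Table 24.

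The change is one line in the list plus its mappings, and the planned sample sizes are unaffected. The downside is the possible loss of a few deaths coded only as O36.2. Accepting O36.2 with a recorded non-live outcome limits that loss. Requiring a listed death code does not, because those codes already make the pregnancy an event.

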The highest SLE severity classification experienced by a patient in the baseline period (maximum look-back period of 12 months prior to LMP2) and highest activity (maximum look-back period of 6 months prior to LMP2 and at the end of each trimester for the adverse birth outcomes) will be assessed using the severity and activity algorithms (Figure 7 and Figure 8). The severity algorithm will be used in the selection of the study population (see Figure 5) and each single component of the severity and activity algorithms will be considered for confounding adjustment.

[figure not shown]

Figure 7: SLE disease severity algorithm¹⁶

- SLE-related moderate manifestations: acute pancreatitis, chorioretinitis, demyelinating syndrome/acute inflammatory demyelinating polyradiculoneuropathy, episcleritis/scleritis, hemolytic anaemia, hepatitis (non-viral), ischaemic necrosis of bone, nephritis, renal impairment other than nephritis or end-stage renal disease, lupus enteritis/colitis, mononeuropathy/polyneuropathy, myelopathy, myocarditis, pericarditis, pleurisy/pleural effusion, pseudotumor cerebri, seizure, uveitis vasculitis (excluding aortitis)
- If a severe condition exists, the patient(s) will be moved to the severe category
- Rituximab (including reference product and biosimilars)
- SLE-related severe manifestations: acute confusional state/psychosis, aortitis, arterial/venous thrombosis, aseptic meningitis, cardiac tamponade, cranial neuropathy, intestinal pseudo-obstruction, end-stage renal disease, optic neuritis, pulmonary haemorrhage, stroke/transient ischaemic attack (TIA)

¹⁶ SLE-related manifestations further details are provided in Table 26. Abbreviations: IV, Intravenous; SLE, Systemic lupus erythematosus.

Periods of increased disease activity (flares, [Figure 8](#)) are categorised as mild, moderate and severe ([66](#)), if meeting one or all of the following criteria ([Figure 8](#)), and will be assessed as the highest disease activity experienced by a patient in the baseline period (maximum look-back period of 6 months prior to LMP2). Periods of increased SLE disease activity will also be assessed at the end of each trimester for the adverse birth outcomes. Other markers of disease activity will be retrieved whenever available: results of complements (C3, C4) ([5](#), [43](#)) or anti-double stranded DNA (anti-dsDNA) ([43](#)).

[figure not shown]

Figure 8: SLE disease activity algorithm¹⁷

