	Ascariasis	B77
	Strongyloidiasis	B78
	Trichuriasis	B79
	Enterobiasis	B80
	Other intestinal helminthiasis, not elsewhere classified	B81
	Unspecified intestinal parasitism	B82

Adverse outcomes	Description	ICD-10
	Other helminthiases	B83
	Pediculosis and phthiriasis	B85
	Scabies	B86
	Myiasis	B87
	Other infestations	B88
	Unspecified parasitic disease	B89
	Sequelae of tuberculosis	B90
	Sequelae of poliomyelitis	B91
	Sequelae of leprosy	B92
	Sequelae of other and unspecified infectious and parasitic diseases	B94
	Streptococcus and staphylococcus as the cause of diseases classified to other chapters	B95
	Other specified bacterial agents as the cause of diseases classified to other chapters	B96
	Viral agents as the cause of diseases classified to other chapters	B97
	Other specified infectious agents as the cause of diseases classified to other chapters	B98
	Other and unspecified infectious diseases	B99
	Acute nasopharyngitis [common cold]	J00
	Acute sinusitis	J01
	Acute pharyngitis	J02
	Acute tonsillitis	J03
	Acute laryngitis and tracheitis	J04
	Acute obstructive laryngitis [croup] and epiglottitis	J05
	Acute upper respiratory infections of multiple and unspecified sites	J06
	Influenza due to identified zoonotic or pandemic influenza virus	J09
	Influenza due to identified seasonal influenza virus	J10
	Influenza, virus not identified	J11
	Viral pneumonia, not elsewhere classified	J12
	Pneumonia due to Streptococcus pneumoniae	J13
	Pneumonia due to Haemophilus influenzae	J14
	Bacterial pneumonia, not elsewhere classified	J15
	Pneumonia due to other infectious organisms, not elsewhere classified	J16
	Pneumonia in diseases classified elsewhere	J17
	Pneumonia, organism unspecified	J18
	Acute bronchitis	J20
	Cellulitis	L03
	Glomerular disorders in infectious and parasitic diseases classified elsewhere	N08.0
	Acute tubulo-interstitial nephritis [exclude pyelonephritis]	N10

Adverse outcomes	Description	ICD-10
	Tubulo-interstitial nephritis, not specified as acute or chronic	N12
	Pyonephrosis	N13.6
	Renal and perinephric abscess	N15.1
	Renal tubulo-interstitial disorders in diseases classified elsewhere	N16
	Calculus of urinary tract in diseases classified elsewhere	N22
	Late syphilis of kidney	N29.0
	Other disorders of kidney and ureter in infectious and parasitic diseases classified elsewhere	N29.1
	Acute cystitis	N30.0
	Bladder disorders in diseases classified elsewhere	N33
	Urethritis and urethral syndrome	N34
	Urinary tract infection, site not specified	N39.0

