	Inflammatory diseases of prostate	N41
	Infected hydrocele	N43.1
	Orchitis and epididymitis	N45
	Infections of genitourinary tract in pregnancy	O23
	Other infection during labour	O75.3
	Puerperal sepsis	O85
	Other puerperal infections	O86
	Infections of breast associated with childbirth	O91
	Maternal infectious and parasitic diseases classifiable elsewhere but complicating pregnancy, childbirth and the puerperium	O98
Emergency caesarean section	Delivery by emergency caesarean section	O82.1

Abbreviations used in the table: ICD-10, International statistical classification of diseases tenth revision

Table 25: Adverse birth outcomes, EXEMPLARY codelist

Adverse outcomes	Description	ICD-10
Preterm birth	Preterm spontaneous labour with preterm delivery	O60.1
	Preterm delivery without spontaneous labour	O60.3
	Extreme immaturity	P07.2
	Other preterm infants	P07.3
Small for gestational age	Small for gestational age	P05.1

Abbreviations used in the table: ICD-10, International statistical classification of diseases tenth revision

Table 26: SLE-related comorbidities - for the SLE severity and activity algorithms, EXEMPLARY Code list

Condition severity	Group	Description	ICD-10
Moderate comorbid conditions	Cardiovascular cardiorespiratory system	Haemolytic anaemia	D55-D59
		Myocarditis	I40
		Pericarditis	I30
		Pleurisy/pleural effusion	J90 J91
		Vasculitis (excluding aortitis)	M05.2
	Hepatic and gastrointestinal	Acute pancreatitis	K85
		Hepatitis (non-viral)	K72.0
		Lupus enteritis/colitis	
	Musculoskeletal	Avascular ischaemic necrosis of bone	M87
	Neurological	Demyelinating syndrome/acute inflammatory demyelinating polyradiculoneuropathy	G36-G37
		Mononeuropathy/polyneuropathy	G56-G64
		Myelopathy	G99.2
		Pseudotumour cerebri	G93.2
		Seizure	R56.8
	Ocular	Chorioretinitis	H30.9
		Episcleritis/scleritis	H15
	Renal	Nephritis	N10, N11
Renal impairment (other than nephritis or end-stage renal disease)		S37.0, N18 (excl N18.5)	
Severe comorbid conditions	Cardiovascular cardiorespiratory system	Aortitis	I79.1
		Arterial/venous thrombosis	I82
		Cardiac tamponade	I31.9
		Pulmonary haemorrhage	R04.8
		Stroke (Cerebral Infarction)	I63
		Transient ischaemic attack	G45
	Hepatic and gastrointestinal	Intestinal pseudo-obstruction	K56.0
	Neurological	Acute confusional state/psychosis	F05.1, F05.9
		Aseptic meningitis	G02.0, A87.0, G01
		Cranial neuropathy	S04
	Ocular	Optic neuritis	H46
		End-stage renal disease	N18.5
		Renal failure	N17, N19

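### Tables 24 and 26 give N10 and A87.0 opposite meanings: infection outcome in one list, lupus manifestation in the other, with the N10 bracket excluding the infectious form from the infection list

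*Protocol*

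**What the plan says.** Section 9.3.2 defines the infection outcome as "the first event of a hospitalisation for an infection diagnosis, as primary diagnosis", using the codes in Table 24. That table includes N10, labelled "Acute tubulo-interstitial nephritis [exclude pyelonephritis" (closing bracket follows), and A87, viral meningitis. The outcome belongs to secondary Objectives 8 and 9.

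Table 26 is titled "SLE-related comorbidities - for the SLE severity and activity algorithms, EXEMPLARY Code list". It codes nephritis, a moderate condition, as N10 and N11 without any exclusion, and aseptic meningitis, a severe condition, as "G02.0, A87.0, G01". The notes to Figures 7 and 8 in Section 9.3.3 agree: the moderate manifestations include "ischaemic necrosis of bone, nephritis, renal impairment other than nephritis or end-stage renal disease", and aseptic meningitis is among the severe ones.

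Section 9.3.3 applies the severity algorithm to the 12 months before LMP2 and the activity algorithm to the 6 months before LMP2. It adds: "Periods of increased SLE disease activity will also be assessed at the end of each trimester for the adverse birth outcomes". Severity decides entry at STEP 3 (Section 9.2.2), and each component of both algorithms is a candidate for the propensity score (Sections 9.3.3 and 9.7.1).

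Appendix D opens with a caveat: "Codelists included in this appendix are still under development and will be finalised in the SAP".

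**The concern.** The bracket on N10 acknowledges that the code contains pyelonephritis, then takes out that infection and leaves the remainder in an infection list. Table 26 reads the same code as lupus nephritis. No rule says how an N10 record is to be told apart.

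Two things are at stake. First, the infection outcome loses specificity, and the false events are ones the protocol itself treats as lupus activity. Section 9.7.5 accepts that anifrolumab may reduce disease severity, and Section 9.9 accepts that prescribing depends on severity or activity. The false events may therefore differ between exposure groups, which matters when infection is a safety outcome for an immunosuppressant. Second, the error runs the other way: an infection before pregnancy can be read as a lupus manifestation. This reaches STEP 3, from which the primary cohorts are drawn, as well as the propensity score.

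**Working it through.** **Step 1: the codes side by side.**

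| Code | Table 24 (infection outcome) | Table 26 (SLE algorithms) |
|---|---|---|
| N10 | Listed, pyelonephritis excluded | Nephritis, moderate; no exclusion |
| N11 | Not listed | Nephritis, moderate |
| A87 / A87.0 | A87 listed as viral meningitis | A87.0 listed as aseptic meningitis, severe |
| N12, N16 | Listed; labels name no infection | Not listed |
| O23, N39.0, N13.6, N15.1 | Listed | Not listed |
| M32.1 | Not listed | Not listed (it is an SLE inclusion code in Table 18) |

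Table 24's kidney codes are N08.0, N10, N12, N13.6, N15.1, N16, N29.0 and N29.1. Table 26's renal codes are N10, N11, N17, N18 (with N18.5 separate), N19 and S37.0. N10 is the only one shared. Outside the kidney, A87.0 falls within A87.

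**Step 2: an N10 record during pregnancy.** If N10 is the primary diagnosis of an admission and the case is not pyelonephritis, it is an infection event in Objectives 8 and 9. If it is pyelonephritis, the bracket takes it out of N10. For the adverse birth outcomes, the activity algorithm uses Table 26 at the end of each trimester and reads N10 as nephritis.

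**Step 3: a record before pregnancy.** A kidney infection coded N10 in the 12 months before LMP2 meets the Table 26 code for a moderate manifestation. A viral meningitis coded A87.0 meets the code for a severe one. Either can place a woman in the moderate-to-severe group if nothing else already does so, and either can enter the propensity score as an algorithm component.

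**Step 4: how far this could move the infection risk ratio.** The protocol gives no rate for hospitalised infection or for N10 admissions, so this only illustrates the mechanism. Let p be the comparator risk of true hospitalised infection, f the comparator risk of a false N10 event, and R_inf and R_fl the risk ratios for each. Treating the two kinds of event as additive:

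observed RR = (R_inf × p + R_fl × f) / (p + f)

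Assume p = 4%, R_inf = 1.5 and R_fl = 0.5:

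- f = 0.1%: (0.060 + 0.0005) / 0.041 = 1.48
- f = 0.25%: (0.060 + 0.00125) / 0.0425 = 1.44
- f = 0.5%: (0.060 + 0.0025) / 0.045 = 1.39
- f = 1%: (0.060 + 0.005) / 0.050 = 1.30
- f = 2%: (0.060 + 0.010) / 0.060 = 1.17

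The observed value is a weighted average of R_inf and R_fl. It falls below the true infection ratio when R_fl is smaller than R_inf and rises above it when R_fl is larger, as could happen if anifrolumab goes to women with more active disease.

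**The case against.** The strongest reply is that both tables are marked exemplary, are to be finalised in the SAP, and will be adapted to each source's coding system (Section 9.3). That makes the problem easy to correct, but it does not turn a wrong entry into a detail left open. The tables state incompatible meanings, and an uncorrected entry would be carried into each source's list.

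Several narrower points stand and limit the claim:

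- A reader might infer that lupus kidney flares in general are scored as infections. The documents do not support that. The outcome needs N10 as the primary diagnosis, so flares coded M32.1 or N11 never enter it.
- A reader might infer that kidney infection drops out of the outcome. It need not: O23 (genitourinary infection in pregnancy), N39.0, N13.6 and N15.1 are still listed.
- The severity look-back ends at LMP2 and the outcome starts there, so no single record is both severity criterion and outcome. The in-pregnancy activity assessment is stated for the adverse birth outcomes, not for Objectives 8 and 9. The conflict is in what the code means, not in counting one record twice in one analysis.
- Only A87.0, within 12 months before LMP2, marks a woman as severe. A viral meningitis under another A87 code, or an older one, does not.

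Section 9.9 acknowledges outcome misclassification in general, including differential bias in any direction. It also notes the difficulty of separating active SLE from comorbidity. It does not mention confusion between a lupus flare and the infection outcome.

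**Conclusion.** The point holds in limited form. Followed as written, the lists count non-infectious nephritis admitted under N10 as infection, and they let an infection coded N10 or A87.0 before pregnancy mark SLE severity. Both follow directly from the tables.

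The size is unknown. The range of 1.48 to 1.17 rests wholly on assumed inputs. A reader might take 1.30 to 1.17 as the expected attenuation, but that requires N10 admissions of 1% to 2%, for which the protocol offers no support; at 0.1% the distortion is small. Nor is the direction fixed: it depends on how anifrolumab, and the choice to prescribe it, relate to flares.

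The infection outcome is secondary and outside the meta-analysis, and the sample size and power calculations are unaffected. The STEP 3 route does reach the primary cohorts, but only for women whom no other criterion already classifies as moderate or severe.

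**What to change.** Make these changes when the lists are finalised, before data extraction:

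- **Table 24, N10:** either reverse the bracket so that only pyelonephritis counts, or delete N10 and rely on O23, N39.0, N13.6 and N15.1. Simply dropping the bracket would not do, because non-infectious nephritis would stay in the code.
- **Table 24, N12 and N16:** review both, since neither label names an infection.
- **Table 26, nephritis:** exclude pyelonephritis from the nephritis codes, or require SLE-specific renal coding. M32.1 as described in Table 18 covers organ or system involvement generally, so it would need a renal qualifier.
- **Table 26, aseptic meningitis:** remove A87.0.

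The cost is codelist edits. The downside is slightly fewer coded renal and meningitis records in each list.
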